### 5.3.6 Other Considerations

Not applicable.

## 5.4 Efficacy Analyses

Only “valid days” and “valid seizure counts” will be used in the calculations of seizure frequency per 28 days. A “valid day” is defined as the day where seizure counts information is present, that is, either a record with an answer of ‘No’ to the question ‘Did the subject experience any seizures?’ or a positive number of seizures for at least one of the seizure types collected. “Valid seizure counts” are the seizure counts that are read from the valid seizure days.

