#### 5.1.2 Secondary Endpoints

The following endpoints will be analyzed:

1. The relationship between plasma levels of perampanel and efficacy endpoints (ie, change in average seizure frequency over 28 days, responder probability, and the proportion of subjects who are seizure-free in the Maintenance Period of the Core Study) separately for each seizure type
2. The relationship between plasma levels of perampanel and cognition endpoints including change from baselines in ABNAS, CBCL, and LGPT. In addition, depending on the AE data, the relationship between plasma levels of perampanel and select AEs will be assessed
3. Change from baseline at Week 23 and Week 52 in ABNAS, CBCL, and LGPT
4. Changes from baseline at Week 23 and Week 52 in growth and development parameters (height, weight, thyroid, and IGF-1)
5. Change from baseline in EEG and the frequency of EEG abnormalities during awake and sleep state
6. Proportion of subjects (aged 6 or older at time of consent/assent) with any treatment-emergent reports of suicidal ideation and behavior on the C-SSRS and intensity of these behaviors assessed using C-SSRS scores
7. The median percent change in seizure frequency per 28 days during Treatment Phase (Titration Period and Maintenance Period) of the Core Study, and during the long-term treatment (up to 52 weeks) relative to the Pretreatment Phase. Seizure frequency will be based on the number of seizures per 28 days, calculated as the number of seizures over the entire time interval divided by the number of days in the interval and multiplied by 28
8. Proportion of responders (25% responders defined as a decrease in 28-day seizure frequency of equal or greater than 25% compared to baseline seizure frequency; 50% responders defined as a decrease in 28-day seizure frequency of equal or greater than 50% compared to baseline seizure frequency; 75% responders defined as a decrease in 28-day seizure frequency of equal or greater than 75% compared to baseline seizure frequency) during Maintenance Period of Core Study, and during the long term treatment (up to 52 weeks)
9. Proportion of subjects who are seizure-free during Maintenance Period of Core Study, and during the long-term treatment (up to 52 weeks)
10. CGI of Change

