### 5.4.2 Secondary Efficacy Analyses

The percent change in seizure frequency per 28 days during Treatment Phase (Titration Period and Maintenance Period) of the Core Study with respect to during the Pretreatment Phase will be summarized using descriptive statistics (n, mean, median, minimum, maximum and 95% confidence interval). The percent change in seizure frequency per 28 days are calculated for Total seizure, POS total seizure and total complex partial seizure for POS cohort, for PGTC seizure, absence seizure, myoclonic seizure and total seizure for PGTC cohort and for Secondarily Generalized seizures for GTC cohort. Total Seizures is sum of all seizures, including POS, generalized and other seizures. Total POS Seizures is sum of all POS seizures, including simple partial seizures without motor signs, simple partial seizures

with motor signs, complex partial seizures and complex partial seizures with secondary generalization. Secondly Generalized seizures cohort is a subset of the POS cohort. The proportion of subjects who are seizure-free and the proportion of responders based on decrease from baseline (during the Pretreatment Phase) in 28-day seizure frequency of equal or greater than 25%, equal or greater than 50%, and equal or greater than 75% during Maintenance-LOCF Period of the Core Study will be summarized using frequency count (number and percentage). If subjects complete the Core study and have no seizure during the Maintenance Period, those will be treated as seizure-free.

The number of subjects with new seizure types compared to Baseline Period and Seizure history will be counted.

For analysis for the Japanese submission, all of analysis will be conducted for Japanese population but the following analysis also will be conducted.

The percent change in seizure frequency of POS total seizure per 28 days during Treatment Phase (Titration Period and Maintenance Period) of the Core Study with respect to the Pretreatment Phase will be summarized using descriptive statistics (n, mean, median, minimum, maximum and 95% confidence interval) by 4 week periods (1-4week, 5-8week, 9-12 week, 13-16 week, 17-20 week, 21-23 week, last 4 weeks of treatment).

The CGI-I and CGI-S will be summarized for each visit using frequency count (number and percentage).

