## **8 DEFINITIONS AND CONVENTIONS FOR DATA HANDLING**

### **8.1 EFFICACY DATA HANDLING**

#### **8.1.1 Pre-randomization/baseline efficacy**

All diary data prior to first dose date will be used in the computation of Pretreatment Phase seizure frequency per 28 days. All subjects should have approximately 4 weeks of diary data prior to baseline (Visit 2). The baseline value for other efficacy endpoints will be the last nonmissing measurement occurring prior to the first dose of the study drug.

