#### 5.3.6.2 Efficacy

If no diary data is observed during a period, then the seizure frequency per 28 days for that period will be set to missing. Missing diary data should not be interpreted as equivalent to a non-missing record of zero.

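### Both SAPs drop a diary day answered Yes without a seizure count, so a reported seizure day leaves both the seizure count and the day count

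*SAP*

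**What the plan says.** Core SAP 5.4 states that only valid days and valid seizure counts "will be used in the calculations of seizure frequency per 28 days". There are two routes to a valid day: "either a record with an answer of" No to the question whether the subject had any seizures, "or a positive number of seizures for at least one of the seizure types collected". Valid counts "are the seizure counts that are read from the valid seizure days". Extension SAP 5.4 repeats the definition in the same words.

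Other relevant text:

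- Core SAP 5.1.2 defines frequency without any valid-day restriction: "calculated as the number of seizures over the entire time interval divided by the number of days in the interval and multiplied by 28".
- Core SAP 8.1.1 covers baseline: "All diary data prior to first dose date will be used in the computation of Pretreatment Phase seizure frequency per 28 days". The rule in 5.4 therefore applies before and after the first dose.
- Core SAP 5.4.2 says that completers who "have no seizure during the Maintenance Period, those will be treated as seizure-free".
- Extension SAP 5.3.6.2 adds: "Missing diary data should not be interpreted as equivalent to a non-missing record of zero". The Core SAP has no such sentence.
- Core SAP 5.3.5.1, on missing efficacy data, covers only the Maintenance-LOCF window and outliers.

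**The concern.** The two routes are exhaustive. A diary record that answers Yes but carries no number satisfies neither, so the analysis treats it like a blank day although the caregiver reported a seizure. Nothing in either SAP or the protocol imputes such a day or otherwise keeps it in the analysis. The Extension SAP's statement that missing is not zero does not restore the reported seizure.

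Within the days that carry an answer, the exclusion is informative: it can remove only seizure days, never No days. Two results are exposed. The first is seizure frequency, and through it percent change and responder status. The study is single-arm, so no concurrent control absorbs a difference between periods. Under protocol 9.7.1.6, efficacy for registration in Japan is judged against a fixed 10.5% reduction taken from the placebo arm of another study. The second is the proportion seizure-free, which is an absolute count with no baseline comparison.

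**Working it through.** The plan gives no figure for this point, so there is nothing to reproduce. The inputs from the documents are the valid-day rule (SAP 5.4), the frequency formula (Core SAP 5.1.2) and the 10.5% threshold (protocol 9.7.1.6). The assumed inputs are f, the share of seizure days with no count, and k, the share of all days with a seizure.

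**One child.** Frequency is 28 × S/D, for S seizures in D days. Dropping one day with c seizures gives 28 × (S - c)/(D - 1), which is lower whenever c exceeds S/D.

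- Four single-seizure days in 28: 28 × 4/28 = 4.00. With one uncounted: 28 × 3/27 = 3.11, or -22%.
- Eight days of two seizures in 28: 16. With one uncounted: 28 × 14/27 = 14.5, or -9%.
- The opposite can happen. With 84 seizures in 28 days (three per day), dropping a day with one seizure gives 28 × 83/27 = 86.1. Dropping a day with six gives 28 × 78/27 = 80.9.

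**On average.** If the uncounted days are a random subset of seizure days, seizures are multiplied by (1 - f) and days by (1 - fk). The ratio to the true frequency is (1 - f)/(1 - fk), which never exceeds 1.

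| k | f = 2% | f = 5% | f = 10% | f = 20% |
|---|---|---|---|---|
| 0.05 | -1.9% | -4.8% | -9.5% | -19.2% |
| 0.25 | -1.5% | -3.8% | -7.7% | -15.8% |
| 0.5 | -1.0% | -2.6% | -5.3% | -11.1% |
| 0.8 | -0.4% | -1.0% | -2.2% | -4.8% |
| 1.0 | 0 | 0 | 0 | 0 |

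For example, at f = 10% and k = 0.25 the ratio is 0.90/0.975 = 0.923. A simulation of 20,000 children over 84 days with Poisson daily counts and f = 10% agrees: -8.3%, -3.9% and -0.5% at means of 0.2, 1 and 3 seizures per day. At 3 per day, 40% of the simulated children had a higher frequency under the rule, which matches the exception above.

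**Percent change.** Take one seizure per seizure day and baseline k = 0.30, so the true baseline is 28 × 0.30 = 8.4. With f = 10% it reads 8.4 × 0.90/0.97 = 7.79.

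For a true change of -10.5%, treatment k is 0.2685. The true frequency is 7.52, and with f = 10% it reads 7.52 × 0.90/0.97315 = 6.95. For a true change of -50%, treatment k is 0.15. The true frequency is 4.2, and with f = 10% it reads 3.84.

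| Where 10% of seizure days are uncounted | True -10.5% reads | True -50% reads |
|---|---|---|
| Both periods | -10.8% | -50.8% |
| Treatment only | -17.2% | -54.3% |
| Baseline only | -3.5% | -46.1% |

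**Seizure-free status.** Two readings of Core SAP 5.4.2 are possible. Taken literally, a child with a Yes in the Maintenance Period has had a seizure and is not seizure-free. If the status is programmed from valid counts, a child whose only Maintenance seizure days are uncounted has a total of zero and passes. The text does not choose between them.

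**The case against.** The strongest objection is that no such day may exist. The documents do not show whether the diary or CRF accepts a Yes without a number. Protocol 9.5.1.3 has the investigator review the diary with the parent or guardian at all visits, and telephone calls check completion (protocol Table 4). Detailed derivations sit in separate programming specifications (Core SAP 9). This stands as a limit on size. It is not an analysis rule, and if such records cannot occur the added wording does no harm.

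A second objection is that the same rule governs baseline and treatment. This also stands: equal shares almost cancel in percent change.

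Several stronger inferences are tempting, but the documents do not support them.

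- *The rule favours the drug.* That needs a higher uncounted share on treatment than at baseline. The documents give no share for either period, and the reverse case counts against the drug. The longer treatment period is no argument, because the share of days matters and not their number.
- *Uncounted days are the worst days.* A half-completed entry may equally be a day with one seizure.
- *The valid-day rule as a whole lowers frequency.* Blank days are also invalid, and dropping blank days that were seizure-free raises frequency. The downward direction holds for Yes days without a count, not for the rule overall.
- *A second seizure type reported without a number is scored zero.* The day stays valid through the counted type, but the text does not say how the other type is handled.
- *Such a child will be classed as seizure-free.* The valid-day rule is stated for frequency calculations, and seizure-free status is worded separately. This is an ambiguity, not a rule.

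**Conclusion.** The gap is real. As written, both SAPs remove a reported seizure day from the frequency calculation when no number was entered. Given a random subset of seizure days, the effect on expected frequency is downward: roughly 2% to 10% at f = 10% for k between 0.8 and 0.05, vanishing as seizures become daily. The size in this trial cannot be derived.

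For percent change and responder status, a net bias requires unequal shares in the two periods and can go either way. Against the Japan threshold the illustrated shift is about 7 points in either direction (-17.2% or -3.5% for a true -10.5%). That is an illustration for a frequency ratio; no effect on the confidence limit for the median, which decides the criterion, was calculated. Seizure-free status is the most exposed result, because nothing offsets the error and the wording is open.

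Importance is moderate. The primary objective is safety, Core SAP 5.4.1 lists no primary efficacy analysis, and the Japan criterion is the only formal efficacy decision.

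**What to change.** In section 5.4 of both SAPs, keep the two existing routes and add a third.

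- A day answered Yes with no count is a valid seizure day with a prespecified count of at least 1.
- Name one version as main and the other as sensitivity: a count of 1, or the child's mean count per counted seizure day in the same period (minimum 1). In the four-day example above, a count of 1 restores 4.00. The mean removes the bias when uncounted days are a random subset of seizure days.
- When the seizure type is also blank, use the child's all-seizure mean for total seizures. State what is done for the type-specific series, including total POS, which cannot be imputed by type.
- A child with any such day in the Maintenance Period is not seizure-free.
- Report the number of such days by period.

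The existing routes should stay. Defining validity by an answer to the Yes/No question alone would discard a day with a positive count and a blank answer, which the second route now keeps.

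The cost is one more derivation rule, with no new data collection. Results may be slightly less favourable.

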### 5.4.1 Primary Efficacy Analyses

Not applicable.

### 5.4.2 Secondary Efficacy Analyses

The percent change in seizure frequency per 28 days during Treatment Phase (Titration Period and Maintenance Period) of the Core Study with respect to during the Pretreatment Phase will be summarized using descriptive statistics (n, mean, median, minimum, maximum and 95% confidence interval). The percent change in seizure frequency per 28 days are calculated for Total seizure, POS total seizure and total complex partial seizure for POS cohort, for PGTC seizure, absence seizure, myoclonic seizure and total seizure for PGTC cohort and for Secondarily Generalized seizures for GTC cohort. Total Seizures is sum of all seizures, including POS, generalized and other seizures. Total POS Seizures is sum of all POS seizures, including simple partial seizures without motor signs, simple partial seizures

with motor signs, complex partial seizures and complex partial seizures with secondary generalization. Secondly Generalized seizures cohort is a subset of the POS cohort. The proportion of subjects who are seizure-free and the proportion of responders based on decrease from baseline (during the Pretreatment Phase) in 28-day seizure frequency of equal or greater than 25%, equal or greater than 50%, and equal or greater than 75% during Maintenance-LOCF Period of the Core Study will be summarized using frequency count (number and percentage). If subjects complete the Core study and have no seizure during the Maintenance Period, those will be treated as seizure-free.

The number of subjects with new seizure types compared to Baseline Period and Seizure history will be counted.

For analysis for the Japanese submission, all of analysis will be conducted for Japanese population but the following analysis also will be conducted.

The percent change in seizure frequency of POS total seizure per 28 days during Treatment Phase (Titration Period and Maintenance Period) of the Core Study with respect to the Pretreatment Phase will be summarized using descriptive statistics (n, mean, median, minimum, maximum and 95% confidence interval) by 4 week periods (1-4week, 5-8week, 9-12 week, 13-16 week, 17-20 week, 21-23 week, last 4 weeks of treatment).

The CGI-I and CGI-S will be summarized for each visit using frequency count (number and percentage).

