9.1.2.2 Maintenance Period

During the Maintenance Period of the Core Study (up to 12-week), subjects will continue taking perampanel oral suspension once daily at the dose level they achieved at the end of the Titration Period. (revised per Amendment 02) Multiple dose adjustment is allowed if a subject is experiencing intolerable AE(s) or a higher dose is deemed to be beneficial. All visits are to be done within ± 7 days of the schedule. Each study visit is based on the actual prior visit (eg, Visit 6 is completed 3 weeks ± 7 days of Visit 5, Visit 7 is completed 4 weeks ± 7 days of Visit 6, Visit 8 is completed 4 weeks ± 7 days of Visit 7, Visit 9 is completed 4 weeks ± 7 days of Visit 8). (revised per Amendment 02)

During the Titration and Maintenance Periods, all dose adjustments will be done via 1 dose level up or down. Those who cannot tolerate a minimum of 2 mg dose must discontinue from the study.

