## 5.2 Study Subjects

### 5.2.1 Definitions of Analysis Sets

The **Safety Analysis Set (SAS)** is the group of subjects who received at least 1 dose of study drug and had at least 1 postdose safety assessment.

The **Full Analysis Set (FAS)** is the group of subjects who received at least 1 dose of study drug and had at least 1 postdose primary efficacy measurement.

**PK Analysis Set** is the group of subjects receiving perampanel and with at least 1 quantifiable perampanel concentration at one of the visits during the Maintenance Period of the Core Study and with adequately documented dosing history.

**PK/PD Analysis Set** is the group of subjects receiving perampanel who have seizure frequency, cognition, or AE data with documented dosing history. Subjects receiving perampanel should have at least 1 quantifiable perampanel concentration at one of the visits during the Maintenance Period of the Core Study as per the PK Analysis Set.

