#### 5.3.5 Handling of Missing Data, Dropouts, and Outliers

##### 5.3.5.1 Efficacy

For the last observation carried forward (LOCF) analyses, such as “Maintenance-LOCF” analyses of responder rate, if the overall duration of the Maintenance Period is less than 8 weeks, the diary data up to the last 8 weeks during the Titration and Maintenance Periods combined will be used to calculate the seizure frequency per 28 days for Maintenance-LOCF.

Since data is rank transformed prior to analysis, outliers will have no effect on the calculation for confidence interval of percent change in seizure frequency per 28 days.

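### Core SAP 5.4.2 gives two rules for seizure-freedom, a Maintenance-LOCF window and a completion condition, and they score differently a child who stops early with no seizure in the window

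*SAP*

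**What the plan says.** Core SAP 5.4.2 puts two outcomes into one sentence. It opens with "The proportion of subjects who are seizure-free and the proportion of responders based on decrease from baseline (during the Pretreatment Phase", lists the 25%, 50% and 75% thresholds, and closes with one period for the whole: "during Maintenance-LOCF Period of the Core Study will be summarized using frequency count (number and percentage".

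The next sentence of the same paragraph gives another criterion for seizure-freedom: "If subjects complete the Core study and have no seizure during the Maintenance Period, those will be treated as seizure-free".

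Core SAP 5.3.5.1 defines the LOCF window: "if the overall duration of the Maintenance Period is less than 8 weeks, the diary data up to the last 8 weeks" of Titration and Maintenance combined are used. It sets no minimum amount of diary data and does not require completion. The example it gives is "such as “Maintenance-LOCF” analyses of responder rate"; seizure-freedom is not mentioned there.

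Endpoint 9 in Core SAP 5.1.2 reads "Proportion of subjects who are seizure-free during Maintenance Period of Core Study", with neither LOCF nor completion. Protocol 9.7.1.6 places the seizure-free and responder summaries in the FAS. Core SAP 5.2.1 requires for the FAS only one dose and that the subject "had at least 1 postdose primary efficacy measurement", so early stoppers are in the set.

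Extension SAP 5.4.2 has a parallel completion sentence, but there the period for both outcomes is the plain Maintenance Period of the Extension Phase, without LOCF.

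**The concern.** Two adjacent sentences define the same secondary endpoint, and they do not give every child the same result. Take a child who stops at Week 6 with no seizure in the diary. Under Protocol 9.1.2.1, Maintenance begins only after the 11-week Titration, so this child has no Maintenance data at all. The Maintenance-LOCF sentence nevertheless scores the child seizure-free over the Titration diary. The completion sentence does not.

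The seizure-free proportion for the Core Study therefore has two possible values under the same SAP. The study is open-label and single-arm, so outcomes are visible while data accrue. If the choice is left to programming, it can be made by someone who knows which rule gives the better figure. The LOCF rule also credits children with freedom from seizures in a period they may not have reached, over windows that may be very short.

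**Working it through.** The plan states no figure for this point, so there is none to reproduce. The check applies both rules to each kind of child and then sizes the difference.

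**Step 1: completers.** In Protocol 9.1.2.2, "Each study visit is based on the actual prior visit". Visits 6 to 9 span three intervals of 4 weeks, each ±7 days.
- Shortest scheduled Maintenance: 3 × (28 − 7) = 63 days.
- LOCF trigger: 8 × 7 = 56 days.
- 63 > 56, so for a completer who keeps the windows the fallback is never used and the LOCF window is the Maintenance Period. The two rules agree.

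It follows that a completer with no seizure in Maintenance is already seizure-free under the first sentence. Read as merely sufficient, the second sentence adds nothing. It changes a result only if it restricts seizure-freedom to completers.

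**Step 2: the two rules side by side.**

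| Child | Maintenance-LOCF | Completion rule |
|---|---|---|
| Completes, no seizure in Maintenance | free | free |
| Completes, seizure in Maintenance | not free | not free |
| Stops in Titration, no seizure in window | free | not free |
| Stops after 5 weeks of Maintenance, no seizure in window | free | not free |
| Stops after 10 weeks of Maintenance, no seizure in window | free | not free |
| Stops early, seizure in window | not free | not free |

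The rules part only where a child stops early and has no seizure in the window. In each such row LOCF adds an event, so with a common FAS denominator the difference goes one way.

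**Step 3: size.** Gap in percentage points = 100 × (share who drop out) × (share of dropouts with no seizure in the window). The documents give neither share, so both ranges are assumptions. The planned N of 160 is from Core SAP Section 4.
- Low end: 0.05 × 0.05 = 0.0025, or 0.25 points (0.4 of a child).
- Middle example: 0.10 × 0.20 = 0.02, or 2.0 points (3.2 children).
- High end: 0.20 × 0.50 = 0.10, or 10 points (16 children).

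**Step 4: per child.** This needs no dropout assumption. Core SAP 5.3.4 tabulates efficacy by disease cohort and, within POS and PGTC, by age and EIAED use. One reclassified child moves the rate by 1/40 = 2.5 points among 40 PGTC subjects, and by 1/12 = 8.3 points if the younger PGTC group is at its minimum of 12 (Core SAP 3.2).

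**Step 5: short windows, for scale only.** Assume Poisson seizures at the minimum entry frequency in Protocol 9.3.1 and no drug effect.
- At 1 per 12 weeks, P(no seizure in w weeks) = exp(−w/12): 0.78 at 3 weeks, 0.51 at 8 and 0.37 at 12.
- At 1 per 4 weeks (the Japan criterion), P = exp(−w/4): 0.47, 0.14 and 0.05.

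A shorter window makes an event-free result easier to reach. Children with more frequent seizures would have lower probabilities, so these figures do not size the endpoint.

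**The case against.** The strongest reply is that the SAP can be read without conflict. The LOCF phrase closes the responder clause and may belong to it alone, leaving the next sentence to define seizure-free. The responder-rate example in Core SAP 5.3.5.1, the wording of endpoint 9 and the parallel text in the Extension SAP all fit that reading, and it is probably what was meant. It is still not what 5.4.2 says: seizure-free and responders share one verb and one period. Nothing in the two documents settles the matter, and Core SAP Section 7 is silent. The programming specifications and table shells (Core SAP Sections 9 and 11) may do so, but they are separate documents.

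It is also fair to say that the completion sentence does not contain the word *only*. A reader might infer that the SAP states a completers-only rule outright; it does not. That rule is inferred from Step 1, which shows that the sentence otherwise has no effect.

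Other stronger readings also lack support:
- That every early stopper is scored differently. Those with a seizure in the window are not seizure-free under either rule.
- That LOCF rewards children who left because of intolerance. Protocol 9.5.5 lists categories of discontinuation and gives no frequencies.
- That the trial's conclusions are at risk. The primary objective is safety, and the Japan criterion in Protocol 9.7.1.6 uses the median percent change in POS frequency. Neither depends on this rate.

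Finally, counting all non-completers as not seizure-free is a convention. A labelled sensitivity analysis can carry the alternative.

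**Conclusion.** The point stands as an inconsistency in how a named secondary endpoint is defined. As written, Core SAP 5.4.2 applies Maintenance-LOCF to seizure-freedom and then gives a completion criterion that has effect only as a restriction. The rules disagree for early stoppers with no seizure in the window and for nobody else, provided completers keep the visit windows. With the FAS as denominator for both rules, LOCF can only raise the reported proportion.

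The size cannot be fixed from the documents. The range of 0.25 to 10 points rests wholly on the assumed 5–20% dropout and 5–50% event-free shares. The firmer statement is the weight of one child in a small cohort. The endpoint is descriptive and no pre-specified decision depends on it. The correction is worth making because the rate otherwise has two defensible values.

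**What to change.** In Core SAP 5.4.2, split the sentence so that Maintenance-LOCF applies only to the 25%, 50% and 75% responder rates. Then state one rule for endpoint 9:

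> Seizure-free = completed the Core Study with no seizure in the Maintenance Period; all other FAS subjects count as not seizure-free.

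This fixes the criterion, the handling of non-completers and the denominator together, and it agrees with endpoint 9 and with the responder example in 5.3.5.1. If the LOCF version is wanted, keep it as a labelled sensitivity analysis. The programming specifications and table shells should be checked against the revised text.

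The cost is a small edit to one SAP paragraph. The reported seizure-free rate may be slightly lower than under LOCF.

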9.5.1.3 Efficacy Assessments

Efficacy will be assessed by seizure counts and types as recorded on the diary. Diaries will be dispensed to all subjects at each visit as described in Table 4. The diary is to be completed daily, by the parent/guardian. All seizures will be recorded. At each visit the parent/guardian will be instructed by the site personnel as to how to complete the diary and reminded that they must return the diary at their next scheduled clinic visit and at the Early Discontinuation and Follow-up Visits (if applicable). To ensure correct seizure classification, the medically qualified investigator should review the diary with the parent/guardian at all visits. Parents/guardians must be counseled if diary compliance is not satisfactory (ie, missed three or more consecutive daily diary entries).

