#### 5.4.2 Secondary Efficacy Analyses

The percent change in seizure frequency per 28 days during the Core Study and Maintenance Period of the Extension Phase with respect to baseline assessment collected during the Pretreatment Phase of the Core Study will be summarized using descriptive statistics (n, mean, median, minimum, maximum and 95% confidence interval). The percent change in seizure frequency per 28 days are calculated for total seizure, POS total seizure and total complex partial seizure for POS cohort, for PGTC seizure, absence seizure, myoclonic seizure and total seizure for PGTC cohort and for Secondarily Generalized seizures for GTC cohort. Total Seizures is sum of all seizures, including POS, generalized and other seizures. Total POS Seizures is sum of all POS seizures, including simple partial seizures without motor signs, simple partial seizures with motor signs, complex partial seizures and complex partial seizures with secondary generalization. Secondarily Generalized seizures cohort is a subset of POS cohort.

The proportion of subjects who are seizure-free and the proportion of responders based on decrease from baseline (during the Pretreatment Phase) in 28-day seizure frequency of equal or greater than 25%, equal or greater than 50%, and equal or greater than 75% during Maintenance Period of the Extension Phase will be summarized using frequency count (number and percentage). If subjects complete the Extension Phase and have no seizure during the Maintenance Period, those will be treated as seizure-free.

The number of subjects with new seizure types compared to Baseline Period and Seizure history will be summarized.

The CGIC and CGIS will be summarized for each visit using frequency count (number and percentage).

For Japan submission, all of the analysis will be repeated for Japanese population.

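### Neither SAP makes seizure-free status depend on diary completeness, so among completers blank days can only misclass upward; the net bias is undetermined

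*SAP*

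**What the plan says.** The endpoint is secondary endpoint 9: "Proportion of subjects who are seizure-free during Maintenance Period of Core Study", and likewise over long-term treatment. Core SAP 5.4.2 gives the working rule: "If subjects complete the Core study and have no seizure during the Maintenance Period, those will be treated as seizure-free". Extension SAP 5.4.2 repeats it: "If subjects complete the Extension Phase and have no seizure during the Maintenance Period, those will be treated as seizure-free".

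Protocol 9.5.1.3 names the data source: "Efficacy will be assessed by seizure counts and types as recorded on the diary". In practice, then, having no seizure means having none recorded.

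Three other provisions deal with incomplete diaries.

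- Core SAP 5.4 introduces the valid day, which "is defined as the day where seizure counts information is present". Only valid days and their counts "will be used in the calculations of seizure frequency per 28 days".
- Core SAP 5.3.5.1 has a Maintenance-LOCF rule, which applies "if the overall duration of the Maintenance Period is less than 8 weeks".
- Extension SAP 5.3.6.2 says: "Missing diary data should not be interpreted as equivalent to a non-missing record of zero". It sets the 28-day frequency to missing when a period has no diary data at all. The Core SAP has no equivalent sentence.

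**The concern.** The seizure-free rule has two conditions, completion and no seizure, and neither refers to how much of the diary was kept. A completer with many blank Maintenance days and no seizure on the rest meets both. The effect is close to reading a blank as a zero, which the Extension SAP rejects in principle.

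The direction matters because the study is open-label and single-arm, so no control group with similar diary gaps can offset the error. Children with few seizures, for whom one missed entry can change the classification, are eligible: outside Japan, one qualifying seizure in about 12 weeks is enough (Protocol 9.3.1, criterion 5).

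Seizure freedom is also named in secondary endpoint 1 (exposure and efficacy). Whether it will be modelled cannot be told: Protocol 9.7.1.7.1 names only responder rate and percent reduction, and Core SAP 5.5 leaves the methods to a separate plan.

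**Working it through.** **Does any other text close the gap?**

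- The valid-day rule is limited to the 28-day frequency. Applying it here would not help: once blank days are dropped, a child with no seizure on the remaining days is still seizure-free.
- The Maintenance-LOCF rule deals with a short Maintenance Period, not with gaps in a completer's diary.
- The major deviations named in Core SAP 5.2.3 include study-drug compliance below 80% but nothing on diary compliance.
- Protocol 9.5.1.3 requires counselling after three or more consecutive missed entries. That has no effect on the analysis.

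**Size.** The plan states no expected seizure-free rate, so there is no figure to reproduce. The following is an illustration.

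Inputs: Maintenance of 12 weeks = 84 days (Core SAP 3.2). Assumed, because the documents do not give them: a true rate of r seizures per 28 days, and a share m of days missing at random.

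For a completer with Poisson seizures:

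P(classed seizure-free) = exp[−(r/28) × 84 × (1 − m)] = exp[−3r(1 − m)]

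Example: r = 0.5 and m = 0.10 give exp(−1.35) = 25.9%, against exp(−1.5) = 22.3% with a full diary.

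| r per 28 days | full diary | 10% missing | 20% missing |
|---|---|---|---|
| 1/3 (one per 12 weeks) | 36.8% | 40.7% | 44.9% |
| 0.5 | 22.3% | 25.9% | 30.1% |
| 1 | 5.0% | 6.7% | 9.1% |
| 2 | 0.2% | 0.5% | 0.8% |

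The full-diary column is the true rate under the assumptions. A child with exactly one Maintenance seizure is misclassed with probability m (10% at m = 0.10). With exactly two it is m² (1%).

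If rates vary between children (gamma-distributed with shape k), the proportion for the group is [1 + 3r(1 − m)/k]^(−k). With a mean of 2 per 28 days and k = 1, it goes from 14.3% to 15.6% and 17.2% at 10% and 20% missing. With k = 0.5 it goes from 27.7% to 29.1% and 30.7%. A group with a higher mean rate can therefore still shift by about 1 to 3 points, because it contains low-rate children.

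**The case against.** The strongest case on the other side has five parts.

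1. **The SAP does not say that blank days are seizure-free days.** A reader might infer that it does. The wording is silent on completeness, and the upward misclassification is a consequence of that silence. This stands as a limit on how the point may be put.

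2. **Very incomplete diaries are unlikely in completers.** Diaries are retrieved and reviewed at every Maintenance visit, the investigator goes through them with the parent, gaps trigger counselling, and telephone calls between visits check completion (Protocol 9.5.1.3 and Table 4). It is tempting to illustrate with half-empty or empty diaries, which give large figures, but the documents do not make those cases plausible. An empty diary leaves the Core 28-day frequency with no denominator, and the Extension SAP sets that frequency to missing. The safeguards do not change how a child with some blank days is classed.

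3. **The completion condition works downward.** A child who was seizure-free until dropping out is not credited by the rule. This stands: a reader might infer that the reported proportion is inflated overall, and the documents do not support that.

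4. **The stakes are limited.** The endpoint is a descriptive count and percentage with no success criterion. The primary safety endpoint does not use it, and the Japan criterion rests on median percent change in seizure frequency. This stands.

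5. **A rule may exist elsewhere.** Derivations are held in separate programming specifications (Core SAP 9), which were not available. That is possible, but a condition that defines an endpoint belongs in the SAP.

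**Conclusion.** The gap is real and of moderate importance. As written, both SAPs class a completer as seizure-free when no Maintenance seizure is recorded, whatever share of the diary is blank, and among completers the error can only run upward.

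Its size is unknown because no missing-day rate is given. Under Poisson seizures and days missing at random, the rise at 10% and 20% missing is 3.6 and 7.8 points at 0.5 seizures per 28 days, and 1.7 and 4.1 points at 1. For an individual child at 2 or more it is near zero. The figures depend on why days are blank. If families tend to skip seizure days, the rise is larger. If they skip only uneventful days, there is no misclassification.

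The documents support a claim about missing-day misclassification among completers, and not one about net inflation of the endpoint.

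**What to change.** In Core SAP 5.4.2 and Extension SAP 5.4.2, add a third condition to completion and no recorded seizure: a minimum share of valid diary days in the relevant Maintenance Period, fixed before database lock. An example is 80%, the cut the Core SAP uses for study-drug compliance (5.2.3 and 5.2.6). It is not a diary threshold taken from the documents, and the sponsor may justify another. Class subjects below the minimum as not seizure-free, and report the rate without the minimum as a sensitivity analysis.

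In the same edit, carry the missing-is-not-zero sentence of Extension SAP 5.3.6.2 into the Core SAP. Also reconcile Core SAP 5.4.2 with itself: one sentence summarises seizure freedom over Maintenance-LOCF, and the next defines it for completers over the Maintenance Period.

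The cost is one sentence in each SAP, using data already collected. The reported rate may be slightly lower, and some truly seizure-free children with poor diaries will not be counted; reporting the rate both ways shows how many. A minimum caps the misclassification and does not remove it: a child at 1 seizure per 28 days with exactly 20% of days missing passes an 80% minimum and still has a 9.1% chance of being classed seizure-free, against 5.0% with a full diary.
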